- The procedures must occur on the same day with the ablation occurring prior to the WATCHMAN FLX implant.
- Catheter ablation of the LAA, non-standard ablation techniques (e.g., CFAEs and hybrid ablation) and any non-AF-related ablation (e.g., VT) are not permitted.
- Other concomitant procedures are also not permitted, including, but not limited to, transcutaneous valve procedures, pacemaker, or ICD generator change, etc.

Note: Sequential Ablation subjects who need a repeat ablation cannot combine it with the WATCHMAN FLX implant procedure.

For all patients, CTI ablation and cardioversion may be performed during ablation.

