10.2.2. Randomized

Prior to randomization, the planned ablation procedure type, concomitant or sequential, must be specified. A randomized subject is a subject who signs informed consent and is randomized. Subjects must not be randomized unless they have a valid and signed informed consent and meet all inclusion and no exclusion criteria.

For subjects in the sequential group, randomization can only occur between 90 and 180 days following the most recent AF ablation procedure. Subjects who are planning to have a concomitant procedure must be randomized within 10 days prior to the planned ablation procedure. All subjects (concomitant or sequential) randomized to the Device Group are required to undergo WATCHMAN FLX Device implant within 10 calendar days of randomization. Both groups are followed in accordance with the follow-up schedule. All applicable case report forms per the protocol must be completed. The original signed informed consent and any relevant documentation must be maintained in the site's subject file.

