11.6.1. Sequential Ablation group

Randomization must occur between 90 and 180 days after the most recent AF ablation procedure. If the subject is randomized to the device group, implant must occur within 10 days of randomization.

For roll-in subjects, the implant must occur between 90 and 190 days after the most recent AF ablation.

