11.6.2. Concomitant Ablation group

Randomization must occur within 10 days prior to the planned ablation. If the subject is randomized to the device group, catheter ablation and device implant must occur within 10 days of randomization.

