13.1.2. Primary Safety Endpoint

The Primary Safety Endpoint is Kaplan Meier estimate of time to first occurrence of non-procedural bleeding (ISTH major bleeding and clinically relevant non-major bleeding) through 36 months. Non-procedural events are those occurring after 3 days.

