Additional Analysis	The occurrence of: Stroke Ischemic stroke Hemorrhagic stroke Disabling stroke Non-disabling stroke Systemic embolism Procedural and non-procedural bleeding All-cause death Cardiovascular/unknown death Non-cardiovascular death Device related Thrombus Device Seal Single procedure freedom from AF Healthcare resource utilization Quality of life					
Method of Assigning Patients to Treatment	A subject who signs informed consent is considered enrolled in the study. Subjects will be randomized to OAC or WATCHMAN FLX in equal fashion. Randomization will be stratified by sequential vs. concomitant planned ablation to help ensure balance of treatment assignments within the sequential and concomitant groups.					
Follow-Up Schedule	 Study procedures and follow-up visits will occur as follows: Consent – Must be obtained within 30 days prior to randomization Randomization Prior ablation (Sequential group) – randomization must be performed between 90 and 180 days after the most recent AF ablation procedure. WATCHMAN FLX Implant – must be performed within 10 days following randomization if subject is randomized to the device arm 					

Comparison of Anticoagulation with Left Atrial Appendage Closure after AF Ablation (OPTION)						
	Planned prospective ablation (Concomitant group) – the ablation +/- WATCHMAN FLX Implant must be performed within 10 days of randomization					
	 3 Month Follow-up (90 ± 15 days from randomization) 12-Month Follow-up (365 ± 30 days from randomization) 24-Month Follow-up (730 ± 60 days from randomization) 36-Month Follow-up (1095 + 60 days from randomization) – this follow-up must occur on or after 1095 days and on or before 1155 days Note: for Roll-in subjects the date of implant will be used to calculate Follow-up windows instead of the date of randomization. 					
Study Duration	The duration of the study is expected to last approximately 64 months. The duration of individual subject participation is expected to last approximately 36 months but may vary per subject.					
Control Group Medication Therapy	Following randomization, control subjects must continue or start market-approved OAC used per IFU for atrial fibrillation stroke prevention and should remain on it for the duration of the trial.					

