3.2 Primary Safety Endpoint

The primary safety endpoint is non-procedural bleeding through 36 months (ISTH major bleeding and clinically relevant non-major bleeding). This endpoint is defined as the Kaplan Meier estimate of time to first occurrence of non-procedural ISTH major bleeding or clinically relevant non-major bleeding through 36-months. Non-procedural events are those occurring after 3 days, calculated from implant or attempted implant date for Device patients and from date of randomization for Control patients. This endpoint will be tested for superiority of WATCHMAN vs Control.

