7.3 Rules and Definitions

Binary event rates (proportions) will be calculated on a per patient basis. Two-sided exact 95% confidence intervals will be given for all applicable endpoints presented as proportions.

For all time-to-event analyses, event-free subjects will be censored at the date of their last follow-up. The last follow-up date will be the latest of the following dates for each subject: date of adverse event, randomization date, implant procedure date, discharge date, and follow-up visit date.

Days to (event or censoring date) = (event or censor) date – randomization date.

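### In concomitant-ablation subjects the 3-day procedural window starts at implant in Device but at randomization in Control, so identical ablation bleeds can be excluded in Device and counted in Control

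*SAP*

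**What the plan says.** The primary safety endpoint is time to first non-procedural ISTH major or clinically relevant non-major bleed through 36 months.

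- **Window length.** Protocol 13.1.2: "Non-procedural events are those occurring after 3 days". It gives no starting date.
- **Window start.** SAP 3.2 supplies one, and it differs by arm: "calculated from implant or attempted implant date for Device patients and from date of randomization for Control patients". There is no exception for concomitant ablation.
- **Time origin.** SAP 7.3 computes "Days to (event or censoring date) = (event or censor) date" less the randomization date, in both arms.
- **Concomitant subjects, both arms.** Protocol 11.6.2: "Randomization must occur within 10 days prior to the planned ablation". Protocol 10.2.2 and the SAP synopsis give the same 10-day limit.
- **Concomitant Device subjects.** Protocol Section 8: "The procedures must occur on the same day with the ablation occurring prior to the WATCHMAN FLX implant".
- **Sequential subjects.** Protocol 11.6.1: "Randomization must occur between 90 and 180 days after the most recent AF ablation procedure".

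SAP 3.3.5 makes trial success depend on both the superiority test on this endpoint and the non-inferiority test on the primary efficacy endpoint.

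**The concern.** The exclusion depends only on dates. In the concomitant stratum the procedure that both arms share, the ablation, happens after randomization. In Device the window opens on the ablation day, because the implant is done that day. In Control the window opens at randomization and can close before the ablation takes place. The same bleed after the same ablation can then be a non-event in one arm and a primary safety event in the other.

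The mismatch works in Device's favour in a superiority test. SAP 4.4 relies on each of the two primary tests holding its own level, so part of an apparent benefit in this stratum could come from the date rule. Sequential subjects are not affected, since their ablation was at least 90 days before randomization.

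The point concerns the anchor mismatch only. Implant bleeds later than day 3 still count against Device, so no net direction is claimed for the 3-day rule as a whole.

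**Working it through.** **1. The plan's own figure.** SAP 3.2.2 states 86.4% power for 14% vs 20%, 800 per arm, 20% attrition and two-sided alpha 0.05.

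- HR = ln(0.86)/ln(0.80) = 0.676.
- With exponential event and attrition times, P(event) = λ/(λ+μ) × (1 − e^−(λ+μ)), where λ = −ln(1−rate) and μ = −ln(0.80). This gives 0.180 in Control and 0.126 in Device, 244.7 events in total.
- Power = Φ(√244.7/2 × |ln 0.676| − 1.96) = 86.5%.

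The stated power reproduces. The problem lies in the endpoint definition, not in the power calculation.

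**2. One worked case.** Ablation on day 7 after randomization, bleed on day 8. In Device this is 1 day after implant and is excluded. In Control it is 8 days after randomization and counts.

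**3. How often this happens.** Let a be the ablation day and b the lag from ablation to bleed (0 to 3 days). Device always excludes the bleed. Control counts it when a + b > 3. Over a = 0-10 there are 11 × 4 = 44 pairs. Those not counted number 4 + 3 + 2 + 1 = 10 (a = 0, 1, 2, 3), so 34 of 44 count. As a share of Control ablation bleeds, with ablation days equally likely:

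| Ablation days | Lag uniform 0-3 | All on ablation day |
|---|---|---|
| 0 | 0% | 0% |
| 0-1 | 12.5% (1/8) | 0% |
| 0-3 | 37.5% (6/16) | 0% |
| 0-5 | 58.3% (14/24) | 33.3% |
| 0-10 | 77.3% (34/44) | 63.6% |

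**4. Effect on the test.** The documents do not give the concomitant share, the ablation bleed risk, the lag or the spread of ablation days, so all four are assumed. The log-rank test was simulated with 10,000 trials per scenario, 800 per arm, the same true non-procedural rate (17%) in both arms, 20% attrition, and no implant bleeds after day 3. The entries are Device-favouring rejections in percent, nominal 2.5. Columns are concomitant share / ablation bleed risk.

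| Lag | Days | 25%/1% | 40%/3% | 60%/3% | 60%/6% |
|---|---|---|---|---|---|
| Same day | 0-1 | 2.4 | 2.6 | 2.6 | 2.2 |
| Same day | 0-3 | 2.5 | 2.6 | 2.5 | 2.6 |
| Same day | 0-5 | 2.9 | 3.8 | 5.1 | 8.8 |
| Same day | 0-10 | 3.3 | 6.7 | 8.7 | 22.5 |
| Uniform | 0-1 | 2.7 | 2.7 | 3.3 | 4.2 |
| Uniform | 0-3 | 3.0 | 4.2 | 5.6 | 10.1 |
| Uniform | 0-5 | 2.9 | 5.5 | 7.8 | 18.6 |
| Uniform | 0-10 | 3.2 | 7.3 | 10.8 | 30.2 |

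Reference runs: 2.4% with no windows at all, and 3.0% with the SAP windows but no ablation bleeds. The Monte Carlo standard error is 0.16 points near 2.5% and 0.46 near 30%.

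**5. Extra Control events.** Gross count = 800 × share × risk × fraction counted. Mid case: 800 × 0.40 × 0.03 × 0.773 = 7.4. Worst case: 800 × 0.60 × 0.06 × 0.773 = 22.3. Some of these subjects would bleed later anyway, so the net additions are about 6.3 and 18.8. The planned difference is (0.20 − 0.14) × 800 = 48 events before attrition.

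**6. With the window anchored on the index procedure** (days 0-10, uniform lag), the Device-win rate is 2.6% at 40%/3% and 2.4% at 60%/6%. With no procedural exclusion it is 2.6% in both.

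**The case against.** The strongest objection is that the size rests wholly on assumptions and runs from nothing to about 30%. This stands. The 34 of 44 figure weights day and lag pairs equally and is not an event proportion. Entries around 2.7-3.3% cannot be credited to ablation bleeds, because the SAP windows alone give 3.0%.

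Second, implant bleeds after day 3 count against Device and could offset the effect. In the mid case (days 0-10, uniform lag), adding an assumed 1% of such bleeds brings the Device-win rate to 2.6% under the SAP anchors, and 2% brings it to 0.6%. With the corrected anchor the same cases give 0.7% and 0.1%. The offset is real, but the mismatch still raises the Device-win rate, and one unmeasured bias should not be left to cancel another.

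Third, the plan has safeguards:

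- sequential-versus-concomitant subgroup results with an interaction test (Protocol 13.3.3, SAP 5.2);
- separate reporting whatever the poolability result (SAP 5.4);
- tabulation of procedural and non-procedural bleeding (SAP 3.4);
- a tested secondary endpoint that includes procedural major bleeding (SAP 3.3), though not clinically relevant non-major bleeds.

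These may reveal the artefact. None changes the pooled primary test.

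Fourth, SAP 7.4 makes the Clinical Events Committee's determinations final. Its charter is not in the documents, so a rule based on relatedness to the procedure can be neither assumed nor ruled out. The written SAP rule uses dates only.

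Fifth, SAP 4.1 points the primary safety analysis to Device subjects treated as assigned, with follow-up from the procedure day, which conflicts with a randomization origin. The simulations follow the randomization origin. The asymmetry survives either reading, because neither ties Control to the ablation date.

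**Conclusion.** The concern holds. As written, a rule of one of the two primary tests treats identical ablation bleeds differently by arm in the concomitant stratum, in Device's favour, and no other passage corrects it. Confidence is high for the mechanism.

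The size is unknown from the documents. The mid case (40% share, 3% risk, days 0-10) gives a false Device-win rate of about 7% against 2.5%. The effect is near nil if ablation follows randomization within 0-1 days, and material only if much of the 10-day window is used. About 30% needs a 60% share, 6% risk, full use of the window and spread-out lags together. All of these rates assume no implant bleeds after day 3. It should be fixed before analysis.

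**What to change.** - **Concomitant stratum.** Define procedural bleeding in both arms as events through 3 days after the index procedure (ablation with or without implant), so that Control is anchored on the ablation date. The plan already thinks this way: Protocol Table 11.2-2 defines the index procedure so, and the AF-recurrence definition in SAP 3.4 starts at the later of randomization and index procedure in both arms.
- **Sequential stratum.** Keep the current anchors, so that delayed implant bleeds still count.
- **Sensitivity analysis.** Count all ISTH major and clinically relevant non-major bleeds from randomization with no procedural exclusion. This also recovers Device bleeds between randomization and implant, about one event (800 × 5 days × 1.70e-4 per day = 0.7). It is feasible because the events committee adjudicates from randomization (Protocol 23.3).
- **Related wording.** Reconcile SAP 4.1 (treated as assigned) with SAP 3.2.3 and Protocol 13.2.1 (all randomized, intention to treat). If intention to treat governs, anchor subjects with no index procedure on randomization: sequential Device subjects without an implant or attempt, and concomitant subjects whose ablation is cancelled.

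**Cost.** SAP wording and one clarifying sentence in Protocol 13.1.2. Procedure information is already collected for Device and concomitant subjects. The ablation date is not listed by name, but checking the 10-day limit requires it. Apart from the ablation bleeds that the rule is meant to exclude, the loss is 320 to 480 concomitant Control subjects (40-60% of 800) × 5 days to ablation × 1.70e-4 to 2.04e-4 per day (17-20% over 1095 days) = 0.3 to 0.5 background Control events. No delayed Device implant bleeds are dropped.

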3.2.1 Hypotheses

The objective of the primary safety endpoint analysis is to test the null hypothesis that time-to-event distributions do not differ between the Device and Control groups. The null hypothesis will be tested vs. the 2-sided alternative hypothesis that the time-to-event curves are different.

 H_0 : $S_1(t) = S_0(t)$ H_a : $S_1(t) \neq S_0(t)$,

where $S_1(t)$ and $S_0(t)$ are the time-to-event curves for ISTH major bleeding and clinically relevant non-major bleeding of the Device and Control groups, respectively.

3.2.2 Sample Size for the Primary Safety Endpoint

This sample size was calculated employing log-rank test methodology using EAST 6 software with the following assumptions:

- Expected event rate of the Device group= 14% and of the Control group = 20%
- Alpha = 5% (two-sided)
- Power = 86.4%
- Expected attrition rate = 20%
- Required sample size = 1600 subjects

The expected primary safety endpoint event rate in the Device group is based off the combined PROTECT AF, CAP, PREVAIL, and CAP2 studies' WATCHMAN arms. The observed rate of non-procedural major bleeding at 36 months in these subjects was 9.4%. The primary safety endpoint event rate in the OPTION Device group is then expected to be 14%, which accounts for similar non-procedural major bleeding risk as in previous WATCHMAN studies but with the addition of clinically relevant non-major bleeds unrelated to the implant procedure. The expected rate of 20% in the Control group is based off the rates of major or clinically relevant non-major bleeds reported in the ARISTOTLE, ENGAGE, and ROCKET-AF studies.

Given the above assumptions, 1280 subjects will be required. In order to account for up to 20% expected rate of attrition which includes subjects who die, withdraw, or are lost-to-follow-up through 36 months without experiencing an endpoint event, a total of 1600 (1280/(1-0.2)) subjects need to be enrolled. A sample size of 1600 subjects provides approximately 86.4% power for the Primary Safety Endpoint analysis.

3.2.3 Statistical Methods for the Primary Safety Endpoint

All subjects in the randomized cohort will be included in the analysis. A log-rank test will be performed including all subjects in database at the time of analysis post 36 months. The objective is met if the p-value of the log-rank test is less than 0.05.

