8.2. Treatment Assignment

A subject who signs informed consent is considered enrolled in the study. Subjects will be randomized to OAC or WATCHMAN FLX in equal proportion. Randomization will be stratified by sequential vs. concomitant planned ablation +/- WATCHMAN implantation, to help ensure balance of treatment assignments within the sequential and concomitant groups. The planned ablation procedure type, concomitant or sequential, must be specified prior to randomizing the subject.

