11.6. Randomization

Randomization will occur after all clinical and transthoracic echo criteria have been verified and the baseline assessment is complete. Randomization will occur no later than 30 days following consent. Subjects will be randomized 1:1 (Device: Control) and randomization will be stratified by sequential vs. concomitant planned ablation to help ensure balance of treatment assignments within the sequential and concomitant groups.

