13.1.2.3. Statistical Methods

All subjects in the randomized cohort will be included in the analysis. Log- rank test will be performed including all subjects in database at the time of analysis post 36 months. The objective is met if p-value of the log-rank test is less than 0.05.

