5.1 Description of Baseline Variables

Baseline demographic and clinical variables will be summarized for each of the treatment groups for both the intent-to-treat and per protocol populations. All continuous variables will be summarized as means, medians, standard deviations and interquartile ranges and compared between treatment groups using one-way analysis of variance (ANOVA) or the non-parametric Kruskal-Wallis test. Categorical variables will be summarized as frequencies and percentages and compared between treatment groups using Pearson's χ^2 test or Fisher's exact test, as appropriate. Ordinal variables will be compared using Cochran-Mantel-Haenszel test with row mean scores.

A by-subject listing of key demographic data and baseline characteristics, including variables used for stratification will be provided.

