5.2 Subgroup Analyses

Primary effectiveness and safety endpoint results will be summarized. Additionally, treatment groups compared based on the following subgroups:

- Sequential vs Concomitant patients
- Male vs female
- Age at time of consent (< 75 years vs. ≥ 75 years)
- Stroke risk (CHA₂DS₂-VASc score 2-3, 4-5, and >5)
- Bleeding risk (HAS-BLED scores of 0, 1-2, and > 2)
- AF type at baseline (paroxysmal, persistent, permanent)
- Implanting image techniques (TEE vs CT for core lab data)

Time-to-event curves will be constructed for each treatment group, HRs and log-rank test p-values will be calculated within each subgroup, and subgroup by treatment interactions will be tested using Cox regression.

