5.4 Pooling Analyses

The analyses of the primary effectiveness and safety endpoints will be presented using data pooled across investigational centers and geographic regions. Analyses will be performed to justify this pooling. Poolability will be assessed across site, geographical region, and sequential vs. concomitant ablation for each primary endpoint. Results will also be presented separately for site, geographical region, and sequential vs. concomitant ablations regardless of the results of the poolability assessments. Sites that successfully implanted with 5 subjects or fewer will be considered "small sites" and will be grouped together as one site per geographical region for the purpose of poolability assessment.

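### Randomization is stratified by planned ablation group but the primary safety log-rank is not; the test is valid, and stratifying it is a cheap, optional improvement with a possible downside

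*SAP*

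**What the plan says.** Protocol 11.6 sets 1:1 allocation and says "randomization will be stratified by sequential vs. concomitant planned ablation to help ensure balance of treatment assignments" within the two groups. Protocol 8.2 adds: "The planned ablation procedure type, concomitant or sequential, must be specified prior to randomizing the subject". The factor is therefore known for every randomized subject at time zero.

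The primary safety endpoint is time to first non-procedural ISTH major or clinically relevant non-major bleeding through 36 months. SAP 3.2.3 tests it as follows: "A log-rank test will be performed including all subjects in database at the time of analysis post 36 months". Success is p < 0.05. Protocol 13.1.2.3 gives the same test. SAP 3.2.1 states the null as equality of the overall Device and Control curves. The sample-size assumptions in SAP 3.2.2 are one rate per arm, 14% for Device and 20% for Control, with no strata.

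The ablation factor does appear in supporting work. It is a subgroup in SAP 5.2 ("Sequential vs Concomitant patients"), a covariate in the ancillary Cox models of SAP 5.3, and part of SAP 5.4: "Poolability will be assessed across site, geographical region, and sequential vs. concomitant ablation for each primary endpoint". Neither document says why it is left out of the primary test.

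**The concern.** When randomization is balanced within strata and the strata have different risks, part of the chance variation in the treatment comparison has been removed by design. An unstratified log-rank does not credit that removal, so its variance is slightly too large. It then runs a little below its nominal level and gives up some power against a test that uses the strata.

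The strata could differ in bleeding risk. Sequential subjects had their ablation 90 to 180 days before randomization. Concomitant subjects have theirs within 10 days after it.

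At stake is a small amount of power on one of two tests that must both succeed for the study to succeed (SAP 3.3.5).

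**Working it through.** **Reproducing the stated power.** Inputs from SAP 3.2.2: 14% versus 20% at 36 months, 20% attrition, N = 1600, two-sided alpha 5%.

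- Hazard ratio = ln(0.86)/ln(0.80) = 0.676.
- With exponential event and dropout times, P(event observed) = λ/(λ+μ) × [1 − exp(−3(λ+μ))].
- Device: λ = 0.0503, μ = 0.0744, so 0.4033 × (1 − 0.86 × 0.80) = 0.126. Control: 0.5 × (1 − 0.80 × 0.80) = 0.180.
- Expected events = 800 × (0.1258 + 0.180) = 244.7.
- Schoenfeld power = Φ(√244.7 × |ln 0.676|/2 − 1.96) = Φ(1.10) = 86.5%, against the stated 86.4%.

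**Planned versus stratified test, similar relative effects.** 20,000 simulated trials per scenario, 800 per arm, 1:1 within strata, exponential times, 20% attrition, both tests run on the same data. Overall rates are held at 14% and 20%. Stratum event-rate ratios and lower-risk shares (30%, 50%, 70%) are assumptions. A ratio of 3 with equal strata, for example, means Control rates of 10% and 30%. Device rates follow either a common hazard ratio or a common risk ratio of 0.70.

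| Event-rate ratio | Power, equal strata, common hazard ratio: plain / stratified | Gain over all splits and both effect models (points) | Type I error, plain |
|---|---|---|---|
| 1 | 86.1% / 86.1% | 0.0 | 4.9% |
| 1.5 | not listed | 0.1–0.2 | 4.8–5.0% |
| 2 | 86.3% / 86.9% | 0.3–0.7 | 4.6–5.1% |
| 3 | 86.9% / 88.0% | 0.7–1.9 | 4.3–4.6% |

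The plain test's power is 85.6% to 87.3% in every scenario. The stratified test's type I error is 4.8% to 5.2%. Monte Carlo standard error is about 0.24 points for power and 0.15 for type I error.

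**Unequal effects.** Equal strata, overall rates again 14% and 20%, with 80% of the absolute benefit placed in one stratum. The 6-point overall benefit then splits as 0.8 × 6/0.5 = 9.6 points in one stratum and 0.2 × 6/0.5 = 2.4 in the other.

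- Control risk 20% in both strata (Device 10.4% and 17.6%): stratifying loses about 0.4 to 0.5 points.
- Ratio 2 (Control 13.3% and 26.7%), benefit mostly in the lower-risk stratum (Device 3.7% and 24.3%): 86.0% falls to 83.7%, a loss of about 2.3 to 2.4 points. With 60% of the benefit there instead of 80%, the loss is about 0.8.
- Ratio 2, benefit mostly in the higher-risk stratum: stratifying gains 0.3 to 1.5 points.

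**Non-inferiority tests, for context.** The pooled standard error is overstated by √[p(1−p)/Σ w_k p_k(1−p_k)] − 1. With p = 10% and equal strata at 5% and 15%, this is √(0.0900/0.0875) − 1 = 1.4%. At ratio 3 the range is 0.8% to 2.1% over the splits and both endpoints. The pooled Kaplan-Meier difference is as precise as a stratum-weighted one; only its bound is slightly wide.

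**The case against.** The strongest objection is that nothing here is a defect. A valid, slightly conservative log-rank that matches its own sample-size method is a legitimate choice. Protocol 20.4 expects the combined procedure to carry risks similar to those of the two procedures done separately, so the strata may not differ and the gain may be nil. This stands, and it is why the point is only an option.

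The second objection is that stratifying is not without cost. The gains assume similar relative effects in both strata, and unequal effects are plausible. Under SAP 3.2 the 3-day procedural window runs from implant for Device but from randomization for Control, while a concomitant ablation may come up to 10 days after randomization. An ablation-related bleed can therefore count in a concomitant Control subject when the same bleed in a Device subject is excluded. None of the simulations models such early bleeding. This also stands: the sign of the power change depends on effects that nobody knows yet.

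Third, a stratified test addresses equality within strata, not the overall null in SAP 3.2.1, so that text has to change too.

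A reader might go further and infer that ignoring the strata invalidates the test, inflates type I error or undercuts the 86.4%. The documents do not support that. The stated power was computed from overall rates with no strata, and it reproduces. The error departs from 5% only on the conservative side.

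**Conclusion.** The mismatch between randomization and primary safety analysis is real, and it is harmless to validity. Stratifying the log-rank is a cheap, optional improvement. With similar relative effects, its expected gain runs from nothing to just under 2 points, the upper end needing a 3-fold event-rate ratio. Against that stands a possible loss of about 0.5 to 2.4 points under strong assumed heterogeneity of effect.

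Confidence is high on the plan's wording, the validity of the planned test and the direction of its conservatism. The sizes are conditional on assumed stratum rates and shares and on constant hazards. The point does not carry over to the two non-inferiority analyses. It is also separate from the question of which analysis set applies to the safety endpoint, where SAP 3.2.3 and SAP 4.1 differ.

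**What to change.** If the sponsor takes the option, before the analysis:

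- SAP 3.2.3: make the primary test a two-sided log-rank stratified by planned ablation group as randomized, with the objective still met if p < 0.05. Keep the unstratified log-rank as a sensitivity analysis.
- SAP 3.2.1: state the null as equality of the Device and Control curves within each stratum.
- SAP 5.5 and 5.6: run the safety tipping-point and worst-case analyses with the same stratified test.
- SAP 3.1.3, 3.3.3 and 3.3.6: no change, so the attached non-inferiority simulations remain as they are.

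The cost is a few sentences and one stratification term in the code. Alpha and N stay the same, and no new data are needed: the group is fixed before randomization, and SAP 5.1 already lists key baseline data by subject, "including variables used for stratification will be provided". A small stratum is no obstacle. With 10% of subjects in one stratum (80 per arm) at ratio 2, stratified type I error was 5.1% to 5.2% and the gain 0.1 to 0.4 points.

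Protocol 13.3.10 allows the change through an amended SAP approved before the analysis. Changing Protocol 13.1.2.1 and 13.1.2.3 to match would also need the IRB/EC/REB review and approval that Protocol 18.3 requires for amendments, in a trial with up to 150 sites.
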